## 1. SYNOPSIS

Study Title	Type-2 diabetes: risk perceptions and self-management behaviour	
Internal ref. no. / short title		
Study Design	Pilot study, Questionnaires	
Study Participants	People with Type 2 diabetes, aged 30 to 75	
Planned Sample Size	40	
Planned Study Period	01/06/2017 – 01/10/2017	
	Objectives	Outcome Measures
Primary	To assess the feasibility of a larger study.	Feasibility of study protocol, consent rate, acceptability of intervention, retention rate, rates of missing data.
Secondary	To assess the effectiveness of the intervention in patient's awareness of risks for complications associated with Type 2 diabetes.	Change in risk perception scores.
	To assess whether the intervention encourages the adoption of recommended self-care behaviours.	Change in self-management behaviour scores.

## 2. ABBREVIATIONS

CI	Chief Investigator
CRF	Case Report Form
CTRG	Clinical Trials & Research Governance, University of Oxford
GCP	Good Clinical Practice
GP	General Practitioner
NHS	National Health Service
REC	Research Ethics Committee
T2DM	Type-2 Diabetes Mellitus

## 3. BACKGROUND AND RATIONALE

For the past twenty years, evidence has accumulated about the harmful effects caused by type 2 diabetes. Overall, people with type-2 diabetes (T2DM) have age-specific death rates about twice those of the general population. In particular, they have a higher risk of experiencing cardiovascular diseases.

In the recent literature, there is a consensus that consistent self-management behaviour can delay the onset of complications associated with type 2 diabetes. Several studies have shown that diabetes self-management education - i.e. interventions aiming at improving (multidimensional) self-management in patients – are associated with improved intermediate outcomes (especially glycaemic control) and thus, indirectly, clinical outcomes. [1-6] This might explain why self-management has become the cornerstone for treating T2DM. [7, 8] However, in spite of this consensus, the most effective method to provide diabetes self-management education (SME) is still unclear.

Although many factors are known to influence health behaviours, risk perceptions are thought to play a key role in the behavioural process. People who underestimate their risks may be less likely to adopt recommended behaviours, while overestimating their risks may cause so much anxiety that it hampers people from taking precautionary measures [9]. There is strong evidence supporting the causality of the association between perceived risks and precautionary behaviours; empirical data have shown a highly significant, albeit small-to-moderate, positive association [10-12]. In addition, perceived risks are significant predictors of behavioural intentions [13, 14]. Although behavioural processes are complex, wrong risk perceptions are a major impediment to the adoption of self-care behaviours and, as a result, an additional risk for the occurrence of adverse outcomes.

Recent studies have shown that people with T2DM largely underestimate their risks of developing complications. [15] Existing risk communication interventions have shown mixed results, with many participants barely understanding the explanations of health professionals about risks and having poor recall of risk information [16-18]. In this context, there is a need for better risk communication interventions. [15] Rather than increasing the quantity of information to be communicated ('less is often more' [19]), it is necessary to improve its quality. New interventions that make use of patients' decision-making biases are considered to be very promising in the risk communication field [20-22]. We believe that such interventions, through which personalised risks are communicated, will help to correct erroneous risk perceptions, and, in turn, have a greater impact on self-care behaviours.

Based on the results of recent studies investigating the risk perceptions and risk attitudes of people with T2DM, we have developed a new, tailored risk communication intervention. This intervention aims to increase patients' awareness of their risks for complications associated with T2DM and, in turn, to encourage the adoption of recommended self-care behaviours. The objectives of the full trial are to assess the feasibility and measure the expected impact of such an intervention, in order to inform the design of a larger study (RCT to be conducted in the future).

#### 4. OBJECTIVES AND OUTCOME MEASURES

Objectives	Outcome Measures	Timepoint(s) of evaluation of this outcome measure (if applicable)
To assess the feasibility of a larger study.	Feasibility of study protocol, consent rate, acceptability of	After the study.

	intervention, retention rate, rates of missing data.	
To assess the effectiveness of the intervention in patient's awareness of risks for complications associated with Type 2 diabetes.	Change in risk perception scores.	
 
• Baseline (right before the intervention).
 
• Baseline (right after the intervention).
 
• After 12 weeks.
 

To assess whether the intervention encourages the adoption of recommended self-care behaviours.	Change in self-management behaviour scores.	
 
• Baseline (right before the intervention).
 
• After 12 weeks.
 

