### **8. STATISTICS AND ANALYSIS**

#### **8.1. Description of Statistical Methods**

Frequencies and percentages will be used to describe categorical variables, and means  $\pm$  SD to describe continuous variables.

Pre-post intervention differences between groups in terms of study outcome variables will be tested using Chi-square and Student t-tests, whereas pre-post intervention differences within groups will be tested using McNemar and paired t-tests.

The Kappa test will be used for detecting the degree of agreement between pre- and post-perceived risk with baseline objective risk.

In the intervention group, correlation between appropriateness of risk perceptions and self-management scores (post-intervention) will be tested by means of point biserial correlation. Finally, Pearson and Spearman correlations will be used to test for correlations between observable characteristics and outcome variables.

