## 8.3. Analysis of Outcome Measures

We will analyse the following outcome variables:

- Feasibility of a larger study: in order to inform the design of a larger study, we will assess the following criteria: integrity of study protocol, consent rate, acceptability of intervention, expected impact of intervention.
- Appropriateness of risk perceptions: we will compare participants' perceived risks to their personalised risk estimates computed via a validated simulation model (UKPDS-OM [32]).
- Self-management scores: we will assess participants' adherence to self-care activities using two validated questionnaires: 1) The Summary of Diabetes Self-Care Activities Measure (SDSCA) [23]; 2) The 8-Item Morisky Medication Adherence Scale (MMAS-8) [33]

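### The risk-perception outcome goes by two names with no cut-off, and its tests are not assigned; a baseline-adjusted distance from the UKPDS-OM estimate would be a better-defined outcome

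*Combined protocol and SAP*

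**What the plan says.** The synopsis and section 4 give the outcome for the risk-awareness objective as "Change in risk perception scores". Section 4 places it before the intervention, immediately after it, and at 12 weeks. Neither section gives a scale or scoring rule.

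Section 8.3 opens with "We will analyse the following outcome variables". Its list has no score change. It has appropriateness of risk perceptions, a comparison of "perceived risks to their personalised risk estimates computed via a validated simulation model". No tolerance, list of complications, time horizon or rule for combining complications follows.

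Section 8.1 has four relevant statements:
- Between arms: "Pre-post intervention differences between groups in terms of study outcome variables will be tested using Chi-square and Student t-tests".
- Within arms: "pre-post intervention differences within groups will be tested using McNemar and paired t-tests".
- Agreement: "The Kappa test will be used for detecting the degree of agreement between pre- and post-perceived risk with baseline objective risk".
- In the intervention arm: "correlation between appropriateness of risk perceptions and self-management scores (post-intervention) will be tested by means of point biserial correlation".

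Section 3 says that under-estimation may discourage recommended behaviour, and also that "overestimating their risks may cause so much anxiety that it hampers people from taking precautionary measures". It presents the intervention as a way to correct wrong perceptions.

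Section 7.3 names no risk-perception instrument or response format. The two references it cites are the self-care and medication-adherence scales.

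**The concern.** Two different variables answer to one objective, and the analysis section does not choose between them. They can disagree. A patient who moves from a large over-estimate to a correct one has improved in accuracy, but on a signed score has moved the opposite way from a corrected under-estimator. A yes/no variable avoids that, but treats a near miss and a gross error alike and depends on a cut-off nobody has written down.

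Three uses of the result are exposed:
- Sections 3 and 8.3 pass the estimated impact to the design of a larger RCT, and section 9.2 allows these data into that trial's analysis.
- Section 7.5 attaches actions to a positive or negative effect on risk perceptions without saying on which variable or in which direction.
- The variable or cut-off could be settled after the data are seen.

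**Working it through.** **1. What the wording implies.** Point biserial correlation needs one two-level variable. Its partner is called scores, so appropriateness is the two-level one. McNemar and Chi-square fit that reading, with t-tests left for the self-management scores. Kappa needs perceived and objective risk in matching categories. Yes/no appropriateness is therefore the likelier reading, and signed change remains open as the literal wording of sections 1 and 4. Even if the between-arm test is on change, baseline is only subtracted, not adjusted for.

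**2. Inputs.** The plan has no figure to reproduce here: no alpha, SD, effect size or share of over-estimators. From sections 6.1 and 8.2: 20 per arm. Everything else is assumed: two-sided 5%; baseline error e0 (perceived minus UKPDS-OM) either in clusters (±1, SD 0.5, share p positive) or normal (SD 1, mean set so that P(e0 > 0) = p). Follow-up error is e1 = k·e0 + N(0, SD 0.5), with k = 0.5 in the intervention arm and 1 in control.

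**3. Analyses compared.** Yes/no: abs(e1) ≤ c, Chi-square without continuity correction. Signed: t-test on e1 − e0. Absolute: t-test on abs(e1) − abs(e0). Adjusted: abs(e1) = b0 + b1·arm + b2·abs(e0), testing b1.

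**4. Power at p = 10%.**

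| Analysis | Clusters | Normal |
|---|---|---|
| Yes/no, c = 0.5 / 0.75 / 1.0 | 37 / 46 / 57% | 25 / 36 / 46% |
| Yes/no, best c from 0.25 to 2.0 | 58% | 66% |
| Improved yes/no, Chi-square | 52% | 63% |
| Signed change, t-test | 59% | 89% |
| Change in absolute error, t-test | 79% | 93% |
| Absolute error, baseline-adjusted | 83% | 97% |
| Category distance (width 1.0), baseline-adjusted | 66% | 88% |

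Repeat runs differed by up to about three points. Type I error of the adjusted analysis was 0.049–0.053.

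**5. Where the gain comes from.** Most comes from not dichotomising. Adjustment adds 83 − 79 = 4 and 97 − 93 = 4 points over the t-test on change in absolute error.

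**6. Effect of the cut-off.** Over c = 0.5–1.0 the yes/no difference runs from 24 to 31 points (clusters) and 18 to 30 (normal): 31/24 = 1.3 and 30/18 = 1.7. Picking the best of these three cut-offs gives 10–11% false positives uncorrected, or about 4% with continuity correction. Also allowing signed change gives 14–15% or 8–9%.

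**7. Offsetting under signed change.** With clusters the expected signed effect is 0.5·(1 − 2p): 0.40 at p = 10% and 0.30 at 20%; simulation gave 0.404 and 0.303. Change in absolute error gave 0.437 and 0.440. Losses: 1 − 0.404/0.437 = 8% and 1 − 0.303/0.440 = 31%. With normal errors: 0.637 against 0.639 (nil) and 0.421 against 0.475 (11%). At p = 5% neither shape shows a loss.

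**8. Check under different assumptions.** For a true shift of 0.8 SD at 20 per arm, a dichotomised outcome has power 0.37–0.50. The continuous follow-up score has 0.72. Baseline adjustment, which multiplies the SD by √(1 − r²), gives 0.76, 0.83 and 0.94 at r = 0.3, 0.5 and 0.7. The ordering is the same.

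**The case against.** The strongest reply is that this is a secondary outcome of a 40-person pilot whose primary aim is feasibility. Power comparisons are then a weak argument, and absolute error is one reasonable choice among several. That stands as a limit on severity. It does not answer the mismatch between sections 1 and 4 and section 8.3, nor the use of the estimate in the next trial.

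It is also fair that section 8.1 can be read as a Chi-square on improvement from baseline rather than on follow-up status. That version reaches 52% and 63%, still below the distance analyses.

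Four stronger readings are tempting and are not supported:
- A reader might infer that the unwritten cut-off could change the reported effect several-fold. That needs cut-offs from 0.25 to 2.0, the upper end calling an error twice the typical baseline error appropriate. Over 0.5–1.0 the ratio is 1.3 to 1.7.
- A reader might infer that absolute error always wins. With no over-estimators and noisy answers (SD 0.7, clusters), signed change does somewhat better: 57% against 52% when half the error is corrected, 83% against 74% at 70% correction.
- A reader might infer that signed change must lose information. The documents say only that patients mostly under-estimate. If over-estimators are few, the loss is nil.
- A reader might infer that absolute error can certainly be computed from the planned answers. No response format is given and Kappa hints at categories, in which case only a category distance is available.

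**Conclusion.** The point holds as a matter of definition and choice of analysis. The outcome has two names that are not interchangeable, no cut-off, no assignment of tests to variables, and no baseline adjustment between arms. A distance from the UKPDS-OM estimate, adjusted for its baseline value, matches section 3's aim of correcting errors in either direction and keeps the size of the error. That ordering held under both assumed error shapes at 10% over-estimators. The power figures are illustrations, because the documents supply none of the inputs except 20 per arm. The consequence is moderate: an ill-defined effect estimate for the later RCT and an undefined trigger in section 7.5, not a failure of the pilot's primary aim. It should be changed before data are seen.

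**What to change.** In sections 1, 4 and 8.3 name one variable: the distance between perceived risk and the baseline UKPDS-OM estimate, lower being better. Use the absolute difference if perceived risk is collected numerically, or the number of categories off if it is collected in ordered categories. State that both refer to the same complications and time horizon, how complications are combined, and which timepoint leads.

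In section 8.1 compare arms by regression of follow-up distance on arm and baseline distance, with a 95% CI, using a robust or transformed version if the distance is skewed. List which test goes with which variable. Keep signed change, yes/no appropriateness with a stated cut-off, and Kappa by arm as descriptive outputs. Report the baseline shares of under- and over-estimators, which the later RCT needs. Refer section 7.5 to the named variable and its direction.

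The cost is wording, with no new visits. Two conditions must be met. Perceived risk must be elicited on the UKPDS-OM scale or in matching categories. The estimate must also be computed for control participants: section 8.3 and Kappa imply this, but section 7.4 describes the calculation only within the intervention. The known drawbacks are skewness and slight attenuation from response noise (in the illustration 0.44 against 0.50 noise-free with clusters, 0.63 against 0.69 with normal errors).

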## 5. STUDY DESIGN

We have designed a pilot study to assess the feasibility and measure the impact of a risk communication intervention for people with T2DM on risk perceptions and self-management behaviour. The intervention has been developed in collaboration with both health professionals and patients.

## 6. PARTICIPANT IDENTIFICATION

### 6.1. Study Participants

40 participants will be recruited (20 in the intervention group, 20 in the control group).

### 6.2. Inclusion Criteria

- Participant is willing and able to give informed consent for participation in the study.
- Aged between 30 and 75.
- Diagnosed with Type-2 diabetes.

The rationale for the lower age limit (30) is that the disease is rarely diagnosed before that age. The rationale for the upper age limit (75) is to be in line with similar existing studies.

### 6.3. Exclusion Criteria

- If unable to provide informed consent.
- If non-English speaker.
- If not suitable for the study according to GP.

## 7. STUDY PROCEDURES

### 7.1. Recruitment

Potential participants will be identified by their GP at [name] practice, Oxford.

Patients willing to participate in the study will be notified during their regular clinical appointments and research visits will be set up to coincide with patients' appointments.

### **7.1. Screening and Eligibility Assessment**

The GP will screen his records in order to identify eligible patients.

### **7.2. Informed Consent**

A patient information sheet; detailing no less than the exact nature of the study, what it will involve for the participant, the implications and constraints of the protocol, and any risks in taking part; will be given to eligible patients during their regular clinical appointment. It will be clearly stated that the study is optional and that the participant is free to withdraw without a reason at any time without prejudice to future care or affecting their rights. The GP will also explain the study and answer potential questions.

Patients willing to participate in the study after reading the patient information sheet will let their GP know and research visits will be set up to coincide with the patients' next appointments, approximately 6 weeks after approach. The CI will meet with the patient to discuss the study, answer any questions they have and receive written informed consent, in the form of a participant dated signature and the dated signature of the CI, to take part.

### **7.3. Procedure**

- Visit 1

For participants who gave their informed consent, the CI will administer the study questionnaires that measures risk perceptions and assesses self-management behaviour (~10 minutes). [23, 33]

After the first set of questionnaires are completed, all participants will attend their routine clinical consultation with their GP. During the consultation, half of the participants will receive the risk communication intervention from the GP (intervention group, ~5 minutes) and half of the participants will not (control group). Participants will be randomised into the intervention or the control group by means of a list drawn up by a computerised randomisation program. They will be attributed with an order number and this number will be randomly allocated into one of the two groups. The participant will be blind to their allocation but the CI will not be.

Right after the consultation, risk perceptions of all participants (i.e. in both groups) will be measured by the CI once again (~5 minutes), to account for potential effect of the consultation on the control group.

- Visit 2

At participants' next consultation visit, which will be approximately 12 weeks after the intervention, the same questions about risk perceptions and self-management behaviour will be asked by the CI right before the consultation (~10 minutes).

The interest of face-to-face appointments is that it ensures reliability in participants' answers, as compared to email or telephone interviews.

This methodology has been used in most recent studies that aimed at measuring the impact of risk communication interventions. [17, 24, 25]

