## **10. QUALITY ASSURANCE PROCEDURES**

The study may be monitored, or audited in accordance with the current approved protocol, GCP, relevant regulations and standard operating procedures.

The CI administering the questionnaires will continually be present with the participants, which will ensure reliable, high quality data to be collected.

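### The CI is unblinded, for no stated reason, while administering face to face every post-intervention risk-perception and self-management measurement; sealed allocations would cheaply reduce the risk of assessor bias, mainly at visit 2

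*Combined protocol and SAP*

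**What the plan says.** Section 7.3 (Procedure) describes randomisation "by means of a list drawn up by a computerised randomisation program". It does not say who holds that list or who tells the GP the allocation. On blinding it says: "The participant will be blind to their allocation but the CI will not be".

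The same section gives the CI all the questionnaire work. The CI administers the baseline set at visit 1. After the consultation, risk perceptions in both groups "will be measured by the CI once again". At visit 2, about 12 weeks later, the risk-perception and self-management questions "will be asked by the CI right before the consultation". The section defends face-to-face contact as more reliable than email or telephone, and says the methodology matches most recent studies of risk communication.

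Section 10 (Quality Assurance) adds: "The CI administering the questionnaires will continually be present with the participants". It offers this as a guarantee of data quality.

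The intervention belongs to the GP, who delivers it (section 7.3) and calculates the personalised estimates (section 7.4). The CI reports back to the GP only after data analysis (section 7.5).

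**The concern.** An interviewer who knows the arm may put questions, prompt or record answers differently in the two groups, without intending to. Blinding the interviewer is the usual protection. Here the plan gives it up in one sentence and does not say why.

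The stakes are limited. The exposed scores are secondary outcomes in a 40-person pilot whose primary objective is feasibility. Two provisions still give them weight. Section 8.3 lists the expected impact of the intervention among the criteria for designing the larger study. Section 9.2 allows the pilot data to enter the larger trial's analysis. A bias in these scores could therefore carry forward.

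**Working it through.** The plan gives no figure to reproduce here. The check is a count of exposure, followed by a comparison of the CI's duties with what blinding would require.

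**1. Measurements exposed** (time points from section 4, assessor from section 7.3)

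| Post-intervention measurement | When | Asked by |
|---|---|---|
| Risk perceptions | Visit 1, right after the consultation | CI |
| Risk perceptions | Visit 2, about 12 weeks | CI |
| Self-management | Visit 2, about 12 weeks | CI |

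- Administered by the unblinded CI: 3 of 3.
- At visit 2: 2 of 3. This share depends on the unit. By contact it is 1 of 2. Counting the two self-management questionnaires in section 8.3 separately, it is 3 of 4.
- For "Change in self-management behaviour scores", section 4 lists one baseline and one later time point. Visit 2 therefore holds 1 of 1 post-baseline measurements, and the between-group comparison of change (section 8.1) rests on that interview.

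**2. Contacts exposed.** Section 6.1 plans 40 participants, 20 per group. With two post-intervention contacts each, 40 × 2 = 80 at most, of which up to 40 are at visit 2. Drop-out would lower both.

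**3. Does any described CI task need the allocation?**

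- Taking consent (section 7.2): no.
- Administering questionnaires (section 7.3): no; both groups get the same ones.
- Calculating estimates and delivering the intervention (sections 7.3 and 7.4): GP tasks.
- Feedback to the GP (sections 7.5 and 9.2): after data analysis.
- Holding the list and passing the allocation to the GP: assigned to nobody.

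No stated task before analysis requires unblinding, but the last item leaves room for an unstated one. The unblinding is explicit. That it can be avoided is partly inferred.

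**4. Where would blinding help most?** Right after the consultation, a participant may mention what was discussed, or the CI may infer the arm from the length of the consultation (the intervention takes about 5 minutes). Visit 2 comes about 12 weeks later and the questions precede that day's consultation, so disclosure is less likely there.

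**5. When could the CI be unblinded?** If the list delivers exactly 20 and 20, releasing each allocation after that participant's visit 2 would let the CI count arms. Once 20 releases in one arm are known, every remaining allocation is known. Even in the best case, the last one follows from the other 40 − 1 = 39. Blinding therefore has to cover all allocations until the last visit 2 questionnaire is recorded and the data are locked.

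**6. Size of bias.** The documents give no standard deviation, effect size or assessor effect, so any bias or false-positive figure would rest wholly on an assumed shift. None is used.

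**The case against.** **The plan gives a rationale.** It defends face-to-face collection and says similar studies used the methodology. Both statements should be acknowledged, but neither explains why the interviewer must know the arm.

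**Standard instruments limit the scope for bias.** Section 8.3 names two validated self-management questionnaires, and the same questions are asked at visit 2. This narrows the route but does not close it when the CI asks in person. For risk perceptions, section 8.3 names a validated model for the comparator, not a validated questionnaire.

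**Participants may know their arm anyway.** This stands. Section 7.2 has the information sheet describe the study fully, and the intervention is a recognisable discussion, so the plan's claim of participant blinding is itself doubtful. The outcomes are self-reported, and sealed allocations would leave this source of bias untouched. They address only what comes from the CI's knowledge.

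**The stakes are modest.** This also stands: the scores are secondary, and pooling with the larger trial is only a possibility.

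A reader might infer three stronger things that the documents do not support:

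- *That every post-intervention outcome is compromised.* Consent, retention and missing-data rates are not interviewer-scored, and the plan does not say who collects acceptability.
- *That the results will favour the intervention.* Nothing in the documents fixes the direction or size of a bias.
- *That the CI can foresee allocations at enrolment.* The plan does not say that the CI holds the list.

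**Conclusion.** The point holds as a cheap improvement. The plan explicitly leaves the CI unblinded, and the CI administers 3 of 3 post-intervention risk-perception and self-management measurements, in up to 80 contacts, with no stated reason and no safeguard. These counts measure exposure; the bias itself cannot be quantified.

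The recommendation assumes that the CI has no undisclosed need for the allocation and that someone other than the CI and the GP can prepare the allocations once. Section 9.2 refers to other researchers on the project but does not say that one is available for this. Confidence is medium for these reasons. The expected gain is mainly at visit 2.

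**What to change.** In section 7.3, replace the clause that leaves the CI unblinded with wording such as:

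> *The CI will remain blind to all allocations until the last visit 2 questionnaire has been recorded and the data are locked. Allocations will be prepared once by a person other than the CI and the GP, and held at the practice in sequentially numbered, sealed form. The GP will open the next allocation only after consent and the baseline questionnaires are complete. The CI will not attend the consultation.*

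In addition:

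- Collect any acceptability answers that would reveal the arm after the visit 2 scores, through the practice or in a form the CI does not see before data lock.
- Do not present participant blinding as assured.
- If the CI must know the allocation, state why and name who holds the list.

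**Cost.** A short amendment, one person to prepare the allocations once, and a small handling task for the practice. There are no extra visits or participants, and no second assessor. Sealing and numbering matter because the GP who opens the allocations also selects patients: "The GP will screen his records in order to identify eligible patients". Opening them after baseline means that the risk estimate must be ready or calculated at that point. Section 8.3 does not limit the estimates to one arm, so this affects timing only.

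**Limits.** Blinding will be imperfect, especially right after the consultation, and bias from participants' own awareness will remain.
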